#### 7.1.1 Unscheduled Visit(s)

An unscheduled visit may be performed at any time during the study as deemed necessary by the investigator. The date and reason for the unscheduled visit will be recorded. AE monitoring and concomitant medication recording should be performed by the investigator. Other procedures and evaluations will be completed as deemed necessary by the investigator and may include (but not limited to) laboratory tests, ECG, vital signs, and physical examination. Please ensure to discuss with the Medical Monitor prior to conducting any unscheduled visit.

#### 7.2 Pandemic Response

In the event of a pandemic that impacts study conduct, the following protocol changes will be implemented should the situation arise (implementation should be discussed on a case-by-case basis, with sponsor approval):

- Visit 1 (Screening), Visit 2 (Pre-baseline, Day -10 to Day -3; Baseline/Day 1), Visit 5 (Week 12), Visit 8 (Week 26), and Visit 9 (Safety follow-up) are considered essential visits, and these visits need to be conducted on-site, with proper site arrangements to protect the safety of study participants and site staff, including personal protection equipment, proper spacing between subjects to avoid crowding and allow proper cleaning, transportation arrangements, etc. (full details will be agreed with the CRO and study sites)
- Visit 3 (Week 2), Visit 4 (Week 6), Visit 6 (Week 16), and Visit 7 (Week 20) should be conducted on-site if conditions permit, but flexibility will be allowed upon agreement between sites, CRO, and sponsor. These visits are to be completed according to one of the following options:
  - a. On-site visit with proper safety arrangements
  - b. Site staff visit to the subject at home
  - c. Travel nurse visits the subject at home
  - d. Tele-health using phone, video call, or others
  - e. Subject goes to local laboratory for biological samples to be taken

Any coronavirus disease – 2019 (COVID-19) vaccinations received before screening and during the study through to the Safety follow-up visit will be recorded, and specific guidance in relation to visits will be provided.

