- k Vital signs (systolic and diastolic BP, orthostatic BP, HR, respiratory rate, and body temperature) will be performed pre-dose on all visits. Supine BP and HR recordings will be made after the subject has been supine for at least 5 minutes. Orthostatic BP will be recorded as follows: the first blood pressure will be the average of 3 measurements recorded after the subject is supine for 5 minutes; the second blood pressure will be recorded after the subject stood for up to 3 minutes.
- 1 Safety labs include chemistry, hematology, urinalysis, and coagulation.
- m Prior and concurrent medications.
- n Subject hearing will be tested to establish suitability for ERP assessment (ability to hear or differentiate the 2 different tones necessary for auditory ERP P300 assessment, using the centrally provided ERP equipment); subjects who wear a hearing aid must remove their hearing aid during the Screening auditory test and during ERP P300 recordings.
- o ERP P300 will be performed at the Pre-baseline visit (Visit 2a, Day -10 to Day -3, no dosing); pre-dose and post-dose at Baseline/Day 1 (Visit 2b), Week 2 (Visit 3), Week 12 (Visit 5), and Week 26 (Visit 8). ERP P300 data should be uploaded for quality check immediately after the completion of the Pre-baseline visit (Visit 2a). ERP P300 will also be performed at Safety follow-up (Visit 9, no dosing).
  - Pre-dose ERP P300 assessments will be performed immediately preceding IMP dose but can be up to 1 hour before dose
    in clinic.
  - Post-dose ERP P300 assessments will be performed at approximately 2 (± 1) hours after dose.
- r Subjects who terminate prior to Visit 9 are to complete same assessments as Visit 8/ET (early termination). For clinical outcome assessments, if completed the assessment within 4 weeks of the ET visit they do not need to be repeated; all safety outcomes and drug accountability should be performed regardless of interval.
- \* At Baseline/Day 1 (Visit 2b), ADAS-Cog13 will be performed pre-dose. For visits after Baseline (except for Safety follow-up when dosing is not applicable), all cognitive assessments will be performed post-dose, in the order of ADAS-Cog13, assessments, with ADAS-Cog13 performed at approximately 1 hour (± 30 minutes) post dose.

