### 1.3 Risk-Benefit Assessment

Whilst qEEG and ERP P300 results in humans are indicative of CNS penetration and target engagement, efficacy in subjects with PDD or DLB (in terms of cognitive, functional, or behavioral improvement) has not been established. Therefore, the benefits to study subjects of participating in this clinical trial are not yet known.

In clinical studies of ATH-1017, single SC administration of 2, 6, 20, 40, 60, and 90 mg in healthy young subjects, and multiple administration of 20, 40, 60, and 80 mg (SC, OD, over 9 consecutive days) in healthy elderly subjects, and 40 mg (SC, OD, over 9 consecutive days) in AD subjects were safe and well tolerated. Injection site reactions included pain, pruritus, and/or erythema, were mild in nature, and resolved without specific therapy. A potential risk for hepatotoxicity identified in nonclinical studies has not been observed in human studies but will be closely monitored in this study. To date, no CNS-specific adverse events have been observed in humans.

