# 5.8 Stopping Criteria

For all subjects, at any time during the study, study treatment should be discontinued and the subject will be withdrawn immediately if any of the following criteria/AEs are recorded:

- ALT or AST  $> 5 \times ULN$  for more than 2 weeks
- ALT or AST  $> 8 \times$  upper limit of normal (ULN)
- ALT or AST > 3 × ULN and total bilirubin > 2 × ULN, or international normalized ratio [INR] > 1.5
- ALT or AST  $> 3 \times$  ULN with symptoms (the appearance of fatigue, nausea, vomiting, right upper quadrant pain or tenderness, fever, rash, and/or eosinophilia > 5%)
- AEs:
  - Any SAE confirmed as probably or definitely related to the IMP
  - Any AE of severe intensity confirmed as probably or definitely related to the IMP and associated with clinically significant findings
     (Note: causality as determined by the Sponsor)

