#### 7 STUDY CONDUCT

- Study procedures and their timing are summarized in the Schedule of Assessments (Table 1).
- Protocol exemptions related to enrollment criteria are only allowed with prior investigator, Medical Monitor, and Sponsor approval, supported by documented agreement from the IRB/IEC.
- Immediate safety concerns should be discussed with the Sponsor immediately upon occurrence or awareness to determine if the subject should continue or discontinue study treatment.
- Adherence to the study design requirements, including those specified in the Schedule of Assessments, is essential and required for study conduct.
- All screening evaluations must be completed and reviewed to confirm that potential subjects meet all eligibility criteria. Screening procedures may be conducted on up to 2 separate dates if necessary to accommodate subject and study center schedule. However, every effort should be made to conduct all procedures as early as possible in the screening period. The investigator will maintain a screening log to record details of all subjects screened and to confirm eligibility or record reasons for screening failure, as applicable.
- Due to the quantitative functional biomarker nature of this study, particular precautions will have to be implemented at each site for the electrophysical assessments, i.e. availability of a dedicated quiet EEG room with controlled lighting and temperature.

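### In a pandemic, Section 7.2 lets Visits 3, 4, 6 and 7 each be completed by tele-health alone, so the liver tests behind the Section 5.8 stopping rules need not be taken

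*Protocol*

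**What the plan says.** Protocol Section 7.2 is a limited exception. It applies only when a pandemic affects study conduct, each use is discussed individually, and the sponsor must approve. It opens by stating that "the following protocol changes will be implemented should the situation arise". Screening, the two baseline visits, Week 12 (Visit 5), Week 26 (Visit 8) and Week 30 (Visit 9) must remain on-site. Visits 3, 4, 6 and 7 (Weeks 2, 6, 16 and 20) "should be conducted on-site if conditions permit, but flexibility will be allowed upon agreement between sites, CRO, and sponsor". The section then says: "These visits are to be completed according to one of the following options". The five options are an on-site visit (a), a home visit by site staff (b), a home visit by a travel nurse (c), "Tele-health using phone, video call, or others" (d), and sampling at a local laboratory (e).

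The other relevant places are:

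- **Table 1** (repeated in SAP Appendix 2) schedules safety labs at all four of these visits. Its footnote reads: "Safety labs include chemistry, hematology, urinalysis, and coagulation". Protocol Table 4 puts ALT, AST, ALP and total bilirubin under biochemistry and INR under coagulation.
- **Section 5.8** says that "study treatment should be discontinued and the subject will be withdrawn immediately if any of the following criteria/AEs are recorded" and then lists four liver criteria.
- **Section 1.3** states: "A potential risk for hepatotoxicity identified in nonclinical studies has not been observed in human studies but will be closely monitored in this study".
- **Section 7** states: "Adherence to the study design requirements, including those specified in the Schedule of Assessments, is essential and required for study conduct".

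**The concern.** A phone or video call cannot yield a blood sample. If option d alone completes a visit, the scheduled ALT, AST, bilirubin and INR values are missing and the Section 5.8 liver rules have nothing to act on. Supply would not be interrupted, because Section 5.3 allows study drug to be shipped directly to the patient, so daily dosing could continue past the missed check.

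What is at stake is subject safety. The liver risk is one the sponsor names itself, and the repeat-dose human experience summarised in Section 1.3 covers 9 consecutive days. The early on-treatment checks at Weeks 2 and 6 are both among the visits that can be converted. No bias between arms is claimed, and no efficacy estimate is affected.

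**Working it through.** **Does the text keep the draw in place?**

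1. Section 7.2 asks for one option out of five. Options d and e stand as alternatives, and no sentence attaches a draw to d.
2. The adherence sentence in Section 7 is general. Section 7.2 is the more specific text and describes its own content as changes to the protocol, so the general sentence does not clearly restore the draw.
3. The four liver criteria in Section 5.8 are: ALT or AST above 5 × ULN for more than 2 weeks; above 8 × ULN; above 3 × ULN with bilirubin above 2 × ULN or INR above 1.5; and above 3 × ULN with symptoms. All four need an enzyme value, and the first three need no symptom.
4. The remaining safeguards would not be prompted by a silent rise. Section 6.4.3 allows extra testing when there is a medical reason, and a repeat test once a value is already abnormal. Its Hy's law alert comes from the central laboratory, so it needs a sample. Section 7.1.1 leaves unscheduled tests to the investigator's judgement. Section 9.1 gives a general duty of safety assessment and names no test. The weekly calls in Section 4.4 can pick up symptoms but not enzymes.

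**How long could the gap be?** The inputs are the safety-lab days in Table 1: Days 1, 14, 42, 84, 112, 140 and 182, each with a ±7-day window after Day 1. The nominal gap is the later day minus the earlier day. The gap at window limits is (later day + 7) minus (earlier day − 7), with Day 1 held fixed.

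| Draws omitted | Interval | Nominal gap (days) | At window limits (days) | Excess over 42 (nominal) |
|---|---|---|---|---|
| None | Visits 4 to 5; 7 to 8 | 84 − 42 = 182 − 140 = 42 | 91 − 35 = 189 − 133 = 56 | 0 |
| Visit 3 | Day 1 to Visit 4 | 42 − 1 = 41 | 49 − 1 = 48 | None; longest gap stays 42 (56) |
| Visit 4 | Visits 3 to 5 | 84 − 14 = 70 | 91 − 7 = 84 | 28 |
| Visit 6 | Visits 5 to 7 | 140 − 84 = 56 | 147 − 77 = 70 | 14 |
| Visit 7 | Visits 6 to 8 | 182 − 112 = 70 | 189 − 105 = 84 | 28 |
| Visits 3 and 4 | Day 1 to Visit 5 | 84 − 1 = 83 | 91 − 1 = 90 | 41 |
| Visits 6 and 7 | Visits 5 to 8 | 182 − 84 = 98 | 189 − 77 = 112 | 56 |

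Four visits, each on-site or by tele-health, give 2⁴ = 16 combinations. Omitting any of Visits 4, 6 or 7 pushes the longest gap above 42 days. Only two combinations do not (nothing omitted, and Visit 3 alone), so 16 − 2 = 14 exceed it.

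The first on-treatment check falls 14 − 1 = 13 days after the first dose as scheduled, 41 days without Visit 3, and 83 days without Visits 3 and 4.

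Of the five draws at which stopping could still prevent later dosing (Visits 3 to 7), only Visit 5 must be on-site. If all four convertible visits are held by tele-health alone, the post-baseline on-treatment draws fall from 6 to 2 (Visits 5 and 8). Within those gaps the criterion requiring more than 2 weeks of elevation cannot be assessed from scheduled labs.

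**The case against.** The best contrary reading is that the list in Section 7.2 concerns where and how a visit is held and leaves its Table 1 content intact. Read literally, option e alone would complete a visit with no adverse event review, C-SSRS or drug accountability, which cannot be meant. Section 7.2 contains no express waiver of labs. Where the protocol does excuse assessments, in Table 1 footnote r on early termination, it says so and keeps all safety outcomes. Sections 7, 7.1 and 9.7 all point to following the schedule as written. The exception also needs several agreements, and a draw could be requested at each.

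Part of this stands. Section 7.2 does not say that labs are waived, and a careful sponsor could ask for a draw each time. But the odd result for option e shows that the wording is defective, not that a draw is required. Footnote r governs early termination only. The adherence statements are general, and those who approve an exception have no stated minimum to enforce.

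The limits on consequence also stand. The 83- and 98-day figures require two consecutive visits by tele-health with no other sampling. Section 1.3 reports no hepatotoxicity observed in humans. Weeks 12, 26 and 30 stay on-site and weekly calls continue. The documents do not show that the exception was used, and SAP Section 6 states that the study was stopped early.

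**Conclusion.** The concern holds. As written, each of Visits 3, 4, 6 and 7 can be completed during a pandemic without the liver tests that the Section 5.8 criteria need. The longest nominal interval between liver tests on treatment rises from 42 days to 56 or 70 when Visit 6, or Visit 4 or 7, is converted alone, and to at most 98 (112 at window limits). Converting Visit 3 alone only delays the first check.

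This rests on two assumptions: that Section 7.2 prevails over the general adherence text for these visits, and that no additional draw is arranged at approval or at the investigator's discretion. It is a weakness in the safety provisions worth correcting. It does not mean that monitoring is absent, and it has no bearing on the treatment comparison.

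**What to change.** In Section 7.2, allow one or more of the listed options in place of one. Add that any tele-health visit must be paired, within its visit window, with the scheduled safety blood draw (at minimum ALT, AST, total bilirubin, ALP and INR) through option b, c or e. This keeps the longest nominal gap at 42 days (56 at window limits) and all 6 post-baseline on-treatment draws.

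The cost is two sentences of protocol wording. No test is added beyond Table 1, and the sampling routes are already permitted. The real downside is some in-person contact for older subjects with dementia during a pandemic. The sponsor would also need to decide what happens to dosing when no draw can be arranged, which this wording does not settle.

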#### 7.3 Concomitant Medications and Treatments

# 7.3.1 Prohibited Treatments During the Study

Concomitant use of the following drugs is excluded within 4 weeks prior to Screening and for the duration of the study. All allowed medications should remain stable throughout the study; for medications affecting cognition, the doses should be stable for at least 4 weeks before Screening and throughout the study, unless otherwise noted.:

- Selegiline and trihexyphenidyl in any form or dosage.
- Memantine in any form, combination, or dosage.
- Donepezil at 23 mg.

The following drugs are prohibited during the study:

• Psychoactive medications (including antipsychotics, tricyclic antidepressants, anxiolytics or sedative hypnotics, including barbiturates) having significant anticholinergic effects and/or believed to affect cognitive function (for exceptions see Section 7.3.2).

- Nicotine therapy (including patches), varenicline (Chantix), or similar therapeutic agent.
- Peripherally acting drugs with effects on cholinergic neurotransmission, e.g., oxybutinin (for exception see Section 7.3.2).
- Systemic immunosuppressants, including systemic corticosteroids, if taken in clinically immunosuppressive doses in the judgment of the investigator (for exceptions see Section 7.3.2).
- Antiepileptic medication.
- Chronic intake of opioid containing analgesics; PRN use is allowed (but not within 72 hours before any cognitive assessment).
- Sedating H1 antihistamines; non-sedating H1 antihistamines are allowed and preferred.
- Systemic moderate to strong CYP3A4 inhibitors (e.g., ketoconazole, itraconazole, fluconazole, cimetidine, clarithromycin, erythromycin, troleandomycin) (see Appendix 1: List of Prohibited Medications for non-exhaustive list).
- Systemic moderate to strong CYP3A4 inducers (e.g., carbamazepine, rifabutin, ritonavir, and St. John's wort) (see Appendix 1: List of Prohibited Medications for non-exhaustive list).

Subjects that use prohibited medications listed above during the double-blind treatment period of the study may be discontinued from study drug.

Note: The discontinuation of a subject due to use of a prohibited medication shall be discussed between the investigator, Medical Monitor, and Sponsor. The investigator should contact the Medical Monitor prior to discontinuing a subject for disallowed medications.

See Appendix 1: List of Prohibited Medications for a non-exhaustive list of prohibited medications.

#### 7.3.2 Permitted Treatments

Any medication or vaccine (including over-the-counter or prescription medicines, vitamins, and/or herbal supplements) that the subject is receiving at the time of enrollment or receives during the study must be recorded along with:

- Indication
- Dates of administration including start and end dates
- Dosage information including dose and frequency

In this study, subjects may be taking a stable dose of acetylcholinesterase inhibitors (e.g., rivastigmine), as long the dose and dosage form have been stable for 3 months prior to Screening and no changes are planned during the study.

Solifenacin is allowed if the subject has received a stable dose for at least 3 months before Screening.

The dosage(s) of other allowed concomitant medications should have been stabilized for at least 4 weeks prior to Screening and should remain constant during the course of the study. For concomitant medications that affect cognition, the dosage(s) must have been stabilized for at least 4 weeks prior to Screening and should remain constant during the course of the study. With the exception of medications listed in the Exclusion Criteria (Section 4.3), in Section 7.3.1, and below, concomitant medications will be allowed at the investigator's discretion. When in doubt, the Medical Monitor should be contacted.

In close communication with the Medical Monitor, low doses of antipsychotics (except clozapine) may be allowed if the subject has received a stable dose for at least 4 weeks before Screening. If these medications are taken on a PRN basis, they should not be taken the morning before any cognitive testing. Pimavanserine and aripiprazole (oral) are allowed.

Low doses (in the judgment of the investigator) of anxiolytics may be given PRN but not the night before any cognitive assessments. Barbiturates are allowed only if given for benign tremor in low doses (in the judgment of the investigator). Zolpidem is allowed.

With the exception of tricyclic antidepressants, irreversible MAO-B inhibitors, and S-ketamine, all other antidepressant medications are allowed.

Immunosuppressants in the form of inhaled steroids, otics, opthalmologics, skin creams, and intra-articular injections are allowed.

Topical application of moderate to strong cytochrome P450 3A4 inhibitors or inducers is allowed.

If the permissibility of a specific medication/treatment is in question, please contact the Medical Monitor.

#### 7.3.3 Other Restrictions

#### 7.3.3.1 Food and Food Supplements

The consumption of grapefruit or grapefruit-containing products is prohibited beginning 7 days prior to the first dose of study medication (Day 1) and during the study.

Food supplements and nutraceuticals with potential effects on cognition, such as Axona, tryptophan supplements, and MCT, are excluded during the study, beginning 7 days prior to the first dose of study medication (Day 1). Tetrahydrocannabinol (THC) is prohibited beginning 4 weeks prior to the first dose of study medication (Day 1) and for the duration of the study.

Cannabidiol (CBD) without THC is allowed but not on the clinical visit days, except for topical applications. CBD use should be recorded as concomitant medication.

## 7.3.3.2 Contraceptives

Sexually active males and females and their partners must ensure that a double barrier method of contraception is used (i.e., condom plus diaphragm, condom or diaphragm plus spermicide gel or foam) for the duration of the study, including the 4-week safety follow-up period.

# 7.4 Subject Withdrawal

A subject's participation in the study may be discontinued at any time at the discretion of the investigator and/or Sponsor, in accordance with his/her best professional judgment. However, it is encouraged that the investigator contacts the Sponsor, when possible, to discuss possible reasons for discontinuation prior to withdrawing a subject from the study. Notification of early subject discontinuation from the study and the reason for discontinuation will be made to the Sponsor and will be clearly documented on the appropriate eCRF.

#### 7.4.1 Discontinuation of Study Treatment

All subjects who permanently discontinue study treatment, for whatever reason, will be withdrawn from the study. Upon discontinuation of study drug, subjects will continue with their original treatment; tapering off study medication is not required.

See the schedule of activities for data to be collected at the time of treatment discontinuation and follow-up and for any further evaluations that need to be completed (Table 1).

#### 7.4.2 Withdrawal from the Study

- A subject may withdraw from the study at any time at his/her own request, or may be withdrawn at any time at the discretion of the investigator for safety, behavioral, compliance, or administrative reasons, including protocol deviations
- Subjects must be discontinued from the study and/or receive no further study treatment, if any of the following criteria are met:
  - o Any of the stopping criteria described in Section 5.8
  - Any AE or safety finding that may jeopardize the subject's health in the investigator's judgment, and which is considered to be at least possibly related to the study drug.
  - Withdrawal of informed consent by subject/legally authorized representative. In the event that a subject's decision to withdraw from the study is motivated by adverse

event(s) or stated lack of efficacy, these reasons should be recorded as the reason for early termination.

- Physician decision
- Non-compliance with study drug
- Site terminated by sponsor
- Repeat incapacity of subject and/or caregiver (in the judgment of the investigator) to properly administer study drug despite training and testing
- o Prolonged or definitive loss of caregiver without adequate replacement
- Nursing home placement
- If the subject withdraws consent for disclosure of future information, the Sponsor may retain and continue to use any data collected before such a withdrawal of consent.
- If a subject withdraws from the study, he/she may request destruction of any samples taken and not tested, and the investigator must document this in the site study records.
- All subjects who prematurely discontinue from the study, i.e., prior to Visit 8 (Week 26), unless the cause is screen failure, should return for an early termination visit and complete all the assessments scheduled for the Week 26 visit (Visit 8); see the schedule of activities (Table 1) for data to be collected.
- Unless the reasons of premature discontinuation prevent further meaningful testing, investigators should make every effort to motivate subjects who discontinue early (and caregiver) to return for a Visit 8 (Week 26) for final assessments

Upon discontinuation of study drug, subjects will continue with their original treatment; tapering off study medication is not required.

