# **5.6** Compliance with Investigational Medicinal Products

IMP compliance will be determined from daily records of IMP administration recorded by the caregiver/support person. If a subject demonstrates consistent poor compliance during the study (< 80%), the investigator should evaluate whether the subject should be discontinued from the study, in discussion with the Medical Monitor. Subjects who are off drug for  $\ge 14$  consecutive days may be prematurely discontinued from the study, in discussion with the Medical Monitor.

The study centers will keep an accurate drug disposition record that specifies the subject kit ID number, number of kits dispensed to each subject, and the date of dispensation.

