## 7.1.2 Modified Intent-to-Treat (mITT) Population

The modified intent-to-treat (mITT) population will include all randomized subjects who took at least one dose of the study medication and who completed both an ADAS-Cog13 and ERP P300 assessment at Baseline and during at least one post-baseline visit. Subjects will be analyzed according to the dose they were randomized to.

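### Protocol 7.4.1 withdraws everyone who stops study drug, so their Week 26 values rest on a best-effort return; 7.4.2 and 5.6 also disagree on whether non-compliance forces a stop

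*Protocol*

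**What the plan says.** **Whether non-compliance forces a stop.** Protocol 7.4.2 says "Subjects must be discontinued from the study and/or receive no further study treatment, if any of the following criteria are met", and one listed criterion is simply "Non-compliance with study drug". It gives no threshold and no reference to another section. The first bullet of the same section says a subject "may be withdrawn at any time at the discretion of the investigator for safety, behavioral, compliance, or administrative reasons". Protocol 5.6 deals with compliance that is consistently below 80%: "the investigator should evaluate whether the subject should be discontinued from the study, in discussion with the Medical Monitor". It adds that subjects off drug for 14 or more consecutive days may be discontinued, again after discussion with the Medical Monitor.

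**What a stop leads to.** Protocol 7.4.1: "All subjects who permanently discontinue study treatment, for whatever reason, will be withdrawn from the study". Section 7.4.2 then asks early leavers to attend an early termination (ET) visit with the full set of Week 26 assessments. Unless testing would no longer be meaningful, it adds that "investigators should make every effort to motivate subjects who discontinue early (and caregiver) to return for a Visit 8 (Week 26".

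**What the analysis does.** SAP 7.1.2 defines mITT by at least one dose plus both measures at baseline and at one post-baseline visit: "Subjects will be analyzed according to the dose they were randomized to". SAP 9.6 assigns ET data to visits by study day. SAP 10.5 compares pooled ATH-1017 with placebo by an unadjusted two-sample t-test on change from baseline. SAP Table 6 enters NA under missing data for the GST score, ADAS-Cog13 and ERP P300 latency.

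**The concern.** Two problems meet here, and they differ in weight.

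The first is a conflict of wording. Two sites that both follow the protocol could handle the same poorly compliant subject differently, one stopping because 7.4.2 says *must*, the other continuing after the review described in 5.6.

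The second matters more and does not depend on the first. The *and/or* in the 7.4.2 lead-in suggests that a subject could stop drug and remain in the study, but 7.4.1 removes that option for any reason for stopping. From then on, the value at the primary time point depends on persuading someone who has been formally withdrawn to come back. If those who do not return differ from those who stay, and do so unequally by arm, the Week 26 comparison no longer describes the arms as randomized. No planned analysis would show it.

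**Working it through.** The sample size of 75 was chosen empirically (Protocol 8.6), so there is no power figure to reproduce. The check sets the texts side by side and then applies simple arithmetic to assumed rates.

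**1. The rule for non-compliance.**

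| Place | Force | Threshold |
|---|---|---|
| 7.4.2, criteria list | must | none |
| 7.4.2, first bullet | may, investigator's discretion | none |
| 5.6, poor compliance | should evaluate, with Medical Monitor | consistently < 80% |
| 5.6, time off drug | may, with Medical Monitor | 14 or more consecutive days |

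Other parts of the plan assume that some non-compliers remain. The per protocol set is the compliant part of mITT (Protocol 8.1.2, SAP 7.1.3), and SAP 10.4 tabulates compliance below 80% against 80% or more.

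**2. Where an ET visit lands.** The SAP 9.6 windows for ERP P300 and ADAS-Cog13 are:

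- Day 2–63: Week 2
- Day 64–112: Week 12
- Day 113–161: Week 20
- Day 162–196: Week 26

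Thus ET at Day 60 counts at Week 2, Day 90 at Week 12, Day 155 at Week 20, and Day 175 at Week 26.

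One ambiguity does not change the result. The text of 9.6 speaks of the closest visit at which the assessment is scheduled, and ERP P300 is not scheduled at Week 20. On that reading an ERP recording after Day (84 + 182)/2 = 133 might go to Week 26. ADAS-Cog13 is scheduled at Week 20, so up to Day (140 + 182)/2 = 161 it stays there, and the Week 26 GST, which needs both, is still missing.

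**3. What happens to a subject who does not return.** If both measures were taken at any post-baseline visit, the subject is in mITT. With no Week 26 value, the subject is not in the Week 26 t-test.

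**4. Size, by assumption.** Let q be the proportion of an arm lost at Week 26 and d how much worse (in SD) those subjects are than the rest. With no drug effect and nobody returning, leaving them out improves the arm's mean by q × d, so

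bias in favor of ATH-1017 = q(active) × d(active) − q(placebo) × d(placebo).

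| q active / placebo | d = 0.5 in both arms | d = 1.0 in both arms |
|---|---|---|
| 10% / 10% | 0 | 0 |
| 20% / 10% | 0.10 × 0.5 = 0.05 SD | 0.10 × 1.0 = 0.10 SD |
| 30% / 10% | 0.20 × 0.5 = 0.10 SD | 0.20 × 1.0 = 0.20 SD |

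If half return, the shift per arm is q × d − [(q/2)/(1 − q/2)] × d. For 20% against 10% this gives 0.0889d − 0.0474d = 0.0415d, about 40% of the figure with no returns.

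If the extra 10% on active are unrelated to prognosis, their d is 0. The active arm's shift is then 0.10 × d, the same as placebo's, and the bias is again about 0.

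**5. Precision.** With 50 against 25 and SD 1, the 95% half-width is 0.488 SD. Losing 10% of both arms (45 and 22.5) gives 0.516, and losing 20% (40 and 20) gives 0.548.

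**The case against.** **The conflict is partly apparent.** The same *must* list contains physician decision, which is itself discretionary, so the list may be meant as a catalog of reasons. Protocol 8.1.2 refers to 5.6 for the meaning of compliant, so a site needing a threshold would look there. This stands in part: a sensible site may well apply 5.6, but the lead-in still says *must*, and one cross-reference would settle it.

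**Section 5.6 does not keep people in either.** It too speaks of discontinuing the subject from the study. This stands in full. All kept under 5.6 against all withdrawn under 7.4.2 is not the real contrast, and the effect of the conflict alone cannot be estimated. The loss of follow-up comes from 7.4.1.

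**A reader might infer a bias toward ATH-1017 and an inflated error rate.** In simulation, full enrolment (50 against 25), the pooled t-test, nobody returning and d of 0.5–1.0 give one-sided error of roughly 4%–6% for 20% against 10%, and 5%–12.5% for 30% against 10%, instead of 2.5%. The top value falls to about 11% if SD is fixed within compliance groups. The documents do not support this as a finding:

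- Higher non-compliance on active drug is only assumed. The one hint is Protocol 1.3, "Injection site reactions included pain, pruritus, and/or erythema, were mild in nature". It gives no placebo comparison, and placebo is also a daily injection.
- At 75 subjects the protocol plans an MMRM, 70 mg first and then 40 mg, which would also use earlier visits. The pooled t-test belongs to the SAP for the stopped study.
- SAP section 8 allows no statistical conclusion, so no decision carries these error rates.

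**Much is already tabulated.** Disposition with reasons, compliance category and n by time point are planned, and SAP 9.1 already includes all collected data, so values obtained after a drug stop count. This stands, but none of these tables shows missing Week 26 values by arm and reason or tests their effect. The MMRM is no safeguard, since SAP 10.5.1 runs it only if the simple summaries look interesting.

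**Conclusion.** The wording conflict is real and minor. The design weakness is 7.4.1 combined with the SAP 9.6 windows: a subject whose ET visit falls before Day 162 has Week 26 values only after a voluntary return, and the plan neither counts nor examines those who do not come back.

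The size and direction of any bias are unknown. It is zero with equal loss and equal prognosis in the arms. It would be 0.05–0.20 SD only under the assumed 20%–30% against 10% losses, d of 0.5–1.0 and no returns, and about 40% of that if half return. Nor do the documents support saying that the choice between 5.6 and 7.4.2 by itself decides who has a Week 26 value, because both routes can end in withdrawal and a returning subject is counted.

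Because the trial stopped early, the point bears on exploratory Week 26 estimates and on any reuse of this protocol text. It is worth considering, not critical.

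**What to change.** (a) **Protocol 7.4.2.** Replace the list item with: *Non-compliance with study drug, if discontinuation is decided under Section 5.6.*

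(b) **Protocol 5.6 and 7.4.1.** In 5.6, refer to discontinuation from study treatment instead of from the study. In 7.4.1, state that a subject who stops drug for any reason, not only non-compliance, stays in the study at least for the Week 26 ADAS-Cog13 and ERP P300 assessments, unless consent is withdrawn or testing would not be meaningful. Covering all reasons matters, since stops for adverse events could equally differ by arm.

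(c) **SAP 10.5.** Report the number in mITT without a Week 26 value by arm and reason. Repeat the Week 26 comparison with those subjects set 0.5 and 1.0 SD worse than their own arm's observed mean (higher is worse on both measures). The estimate then moves by the difference in missing proportions times the shift: 20% against 10% at 1.0 SD moves it 0.10 SD. Filled-in values understate the standard error, so the estimate is what to read.

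**Cost.** (a) and (b) are short wording changes. If 10%–20% of 75 stopped drug (an assumption; 8–15 subjects), (b) adds one already-scheduled visit each. (c) is one table and one repeated comparison. For the stopped trial only (c) can still be applied.
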